8.1. General Methodology

Trial results will be reported according to the Consolidated Standards or Reporting Trials (CONSORT) and the consort extension for Cluster Trials.¹⁴

There is one planned final analysis that will be completed approximately 8-12 weeks after the final patient has completed the trial, allowing for an appropriate time for the data to be collected, cleaned, and prepared for the final analysis. All patients will be included up until they are no longer observed (i.e. end of study form completed).

In secondary outcome analyses no adjustments for multiple testing will be used but a precise, focused interpretation of the individual results for secondary outcomes will be reported. Significance levels used will be 0.05 and 95% confidence intervals will be reported. No formal interim analysis or predefined early stopping rules are planned for this trial.

Descriptive data on recruitment, baseline characteristics and study retention will be presented for the whole trial population and separately by country.

8.2. Patient Flow (CONSORT Diagram)

The flow of centres and patients through the trial stages will be reported in accordance with the CONSORT extension statement for cluster randomised trials (Figure 3).¹⁴ The flow diagram will include the number of patients screened, eligible and entered into the trial at each site, receiving the allocated treatment and included in the primary analysis. This will include the number of clusters randomised and followed up to be in the analysis of the primary outcome and number of patients within these as well. Reasons for ineligibility, non-completion of study (where available), and exclusion from the primary analysis will be summarised.

[figure not shown]

Figure 3: CONSORT chart

¹ Total no. of eligible patients and the number of patients assessed for eligibility not recorded for practical purposes.

Imperial Clinical Trials Unit	ZODIAC STATISTICAL ANALYSIS PLAN – MAIN ANALYSIS	V1 17 th Jan 2024
-------------------------------	--	------------------------------

8.3. Baseline Demographics

Baseline patient characteristics will be cross tabulated according to the randomised group to check for appropriate balance and to provide an overview of the study population. They will be summarised using means and standard deviations or medians and 25th, 75th percentiles for continuous variables, and counts and percentages for categorical variables.

As described in Section 5.2, baseline LLT is defined as LLT prior to admission and will be categorised as none, LLT monotherapy and LLT combination therapy. Combinations will be further classified by number of LLT drugs. In addition, we will present LLT classified by intensity based on expected percentage reduction in LDL-C as categorised in the 2019 ESC/EAS guidelines for the management of dyslipidaemias.¹ An additional category of ‘very high intensity’ is included starting at 65% LDL-C reduction. This is just above the 64% LDL-C reduction of evolocumab 140/420mg, the highest expected LDL-C reduction associated with a monotherapy medication in the ZODIAC study. Combination therapies typically are classified as moderate intensity or higher.

For lipid levels, the baseline value will be defined as the last value recorded before or at the day of hospital admission for ACS whichever is the closest to the day of hospital admission.

No hypothesis testing will be performed to test for differences in baseline characteristics by arm.

We will also examine balance between trial arms for the stratification variables at the cluster level.

8.4. Primary Efficacy Analysis

The primary outcome measure, the proportion of patients treated with combination therapy, or who receive escalated monotherapy, or escalated combination therapy, within 16 weeks of the index ACS (regardless of adherence at 16 weeks) will be modelled using a generalised linear mixed model. This model will use a binomial distribution, log link function and with fixed effect for country and site type (secondary/tertiary care/mixed) and a random effect for study site (as a random intercept). If there is a convergence problem with the log-binomial model, Poisson regression with robust standard errors (modified Poisson regression) will be used. The intervention effect will be reported as a Risk Ratio with a 95% confidence interval. For primary analysis hypotheses will be tested as two-sided with a significance level of 0.05.

$$\log(\pi_{ij}) = \beta_0 + \beta_1 ACSDSS_{ij} + \beta_2 COUNTRY1_{ij} + \beta_3 COUNTRY2_{ij} + \beta_4 Site\ type_{ij} + \beta_5 Site\ type_{ij} + U_j$$

Where:

Imperial Clinical Trials Unit	ZODIAC STATISTICAL ANALYSIS PLAN – MAIN ANALYSIS	V1 17 th Jan 2024
-------------------------------	--	------------------------------

- π_{ij} : probability of combination therapy for the i^{th} patient in j^{th} site
- $ACSDSS_{ij}$: dummy variable for intervention ($ACSDSS_{ij} = 0$ or 1) for patient i in j^{th} site
- $COUNTRY1_{ij}, COUNTRY2_{ij}$: dummy variable for COUNTRY ($COUNTRY_{ij} = 0$ or 1) for patient i in j^{th} site
- $Site\ type1_{ij}, Site\ type2_{ij}$: dummy variable for Site Type ($Site\ type_{ij} = 0$ or 1) for patient i in j^{th} site type
- U_j : random effect for site $j \sim N(0, \sigma_u^2)$

This model will use the modified intention-to-treat population and will include all eligible and randomised patients through use of multi-level multiple imputation. If any participants die within 16 weeks they will be excluded from this primary analysis and any similar secondary outcome analysis but will be included in the time to event outcomes (until censored). We will tabulate mortality by intervention arm.

We define the primary outcome as missing for anyone who does not have full 16 week follow up, unless they have met the primary outcome prior to the time they are lost to follow up. All patients will be followed up and the primary outcome data will be collected unless the participant requests to withdraw from data collection. Missing data will be examined and quantified; this will include the time of withdrawal and tabulation for reasons for non-completion of study by country, site, and arms. Patterns of missingness and relationship between variables and outcome will be explored. The proportion of clusters (sites) with a missing individual outcome will be calculated and reported as the number of entire clusters with a missing outcome divided by the number of clusters randomised.

As mentioned in Section 4.8, some patients may have data reported at 24 weeks only. These data may be used, where appropriate, to derive or impute the LLT medication status at 16 weeks.

Although mixed models are valid under the missing at random (MAR) assumption, we will use the multilevel multiple imputation (MMI) method to impute values for individuals who have missing outcome data. Missing data can be related to the cluster level or at patient level. We define level 1 variables as those relating to the patient as X and Y and Z, and level 2 variables as those relating to the site as A and B.

Using the *JOMO package* in R with missing outcome data we can use an imputation model which is the same as the analysis model. The JOMO package allows imputation on a mix of multilevel continuous and categorical data.¹⁵ This method uses Markov chain Monte Carlo (MCMC) methods to impute missing values. We will run N imputations and combine the estimates using the mitools package. We will impute N datasets based on the percentage of participants with incomplete outcomes, where N is rounded to the nearest 10. A minimum of 5 imputation datasets will be used. We will include at patient level, intervention, outcome,

Imperial Clinical Trials Unit	ZODIAC STATISTICAL ANALYSIS PLAN – MAIN ANALYSIS	V1 17 th Jan 2024
-------------------------------	--	------------------------------

age, sex, and comorbidities (diabetes, time since first CV diagnosis) and at site level, type of site and country in the imputation model. We do not anticipate cluster-level variables to be missing. The appropriateness of the assumption of approximate normality of the random effect of this model will be assessed graphically.

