4.5. Sample Size

It is estimated that in the SoC arm, we expect 7% of patients to be on combined therapy at 24 weeks. This estimate is based on published data (Koskinas et al³) using the ELIPS study cohort which included exclusively ACS patients. A slightly lower proportion of patients (5%) may be expected to be on combination therapy at 16 weeks.

To detect a meaningful difference in proportions from the SoC group of 0.05 to 0.15 in the DSS with 90% power, we require 744 patients in 24 clusters within each arm.

This calculation assumes a two-sided statistical test at the 5% significance level, ICC of 0.1 and clusters of a similar size (31 for each site).

Justification for ICC of 0.1: Based on the article by Campbell et al.⁴, it would be reasonable for a guideline implementation study within primary care to assume an ICC of the order of 0.1 for process variables and an ICC of less than 0.05 for the outcome variable. This is also in line with empirical estimates obtained from an online database with ICC reported for cluster studies that aimed to change practice.⁵ In the database we examined the hypertension guideline interventions, these varied from 0.048 to 0.064. In addition, we have to consider clustering within country; to be conservative we have assumed an ICC of 0.1.

Based on our experience working in this setting we do not expect any loss of clusters. However, drop out may occur within clusters. As data are extracted from routinely collected electronic healthcare records, we expect missing data to be low as it will only be patients who actively request data collection to stop that will have missing outcome data. Considering a conservative approach⁶ and assuming a loss to follow-up rate of 5%, we need a minimum total sample size of 1568. Considering adjusted numbers per cluster we aim to recruit 792 over 24 clusters per arm (a total sample size of 1584).

Imperial Clinical Trials Unit	ZODIAC STATISTICAL ANALYSIS PLAN – MAIN ANALYSIS	V1 17 th Jan 2024
----------------------------------	--	------------------------------

All calculations were done using PASS 2022 software⁷ and applying a method of “Tests for Two Proportions in a Cluster-Randomised Design”.

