4.7. Blinding

Study patients and the analysing statistician will be blinded to the treatment group. Due to the nature of the intervention the study team delivering the intervention will not be blinded.

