8.5.2. Continuous outcome

- LDL-C level (or other lipid measure) closest to 16 weeks between intervention arms.

A linear mixed model with a normal distribution, identity link function will be used with a fixed effect for country and site type (secondary/ tertiary care/mix of both) and a random effect for study site (as a random intercept). We will report adjusted mean difference and 95% confidence interval with p-value. In the case of missing data, multiple imputations will be used to impute the outcome at 16 weeks. Baseline measurements and those taken before 16 weeks will be used for the imputation process

$$y = \beta_0 + \beta_1 ACSDSS_{ij} + \beta_2 COUNTRY1_{ij} + \beta_3 COUNTRY2_{ij} + \beta_4 Site\ type_{ij} + \beta_5 Site\ type_{ij} + \beta_6 BaselineLDL_{ij} + U_j$$

Where:

- y : mean LDL-C (or other lipid measure) in mmol/L
- $ACSDSS_{ij}$: dummy variable for intervention ($ACSDSS_{ij} = 0$ or 1) for patient i in j^{th} site
- $COUNTRY1_{ij}, COUNTRY2_{ij}$: dummy variable for COUNTRY ($COUNTRY_{ij} = 0$ or 1) for patient i in j^{th} site
- $Site\ type1_{ij}, Site\ type2_{ij}$: dummy variable for Site Type ($Site\ type_{ij} = 0$ or 1) for patient i in j^{th} site type
- $BaselineLDL_{ij}$: continuous measure in mmol/L for patient i in j^{th} site
- U_j : random effect for site $j \sim N(0, \sigma_u^2)$

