8.5.3. Binary outcomes

- Proportion of patients' reaching target LDL-C levels, <1.4 mmol/L (<55 mg/dL) by Week 16, proportion of patients who receive combination therapy, proportion of patients who receive escalated monotherapy and proportion of patients who receive escalated combination therapy

This analysis will be for all people with Week 16 follow-up.

We will follow the same approach as described for primary outcome and use log-binomial model or modified Poisson regression with a fixed effect for country and site type (secondary/ tertiary care/mix of both) and a random effect for study site (as a random intercept) to estimate an adjusted Risk Ratio with a 95% confidence interval and p-value.

Imperial Clinical Trials Unit	ZODIAC STATISTICAL ANALYSIS PLAN – MAIN ANALYSIS	V1 17 th Jan 2024
-------------------------------	--	------------------------------

Model assumptions for all models will be examined using residual analysis. Following the recommendations by Parker¹⁶ and Rubin¹⁷ no adjustments for multiple testing will be used but a precise, focused interpretation of the individual results for secondary outcomes will be reported.

$$\log(\pi_{ij}) = \beta_0 + \beta_1 ACSDSS_{ij} + \beta_2 COUNTRY1_{ij} + \beta_3 COUNTRY2_{ij} + \beta_4 Site\ type_{ij} + \beta_5 Site\ type_{ij} + U_j$$

Where:

- π_{ij} : probability of combination therapy (or other binary outcome) for the i^{th} patient in j^{th} site
- $ACSDSS_{ij}$: dummy variable for intervention ($ACSDSS_{ij} = 0$ or 1) for patient i in j^{th} site
- $COUNTRY1_{ij}, COUNTRY2_{ij}$: dummy variable for COUNTRY ($COUNTRY_{ij} = 0$ or 1) for patient i in j^{th} site
- $Site\ type1_{ij}, Site\ type2_{ij}$: dummy variable for Site Type ($Site\ type_{ij} = 0$ or 1) for patient i in j^{th} site type
- U_j : random effect for site $j \sim N(0, \sigma_u^2)$

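### No planned analysis gives an overall DSS effect adjusted for baseline lipid-lowering therapy, although sites recruit knowing their arm and the outcome rule depends on that therapy

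*SAP*

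**What the plan says.** **Primary model.** SAP 8.4 fits a log-binomial mixed model for intensification within 16 weeks, "with fixed effect for country and site type (secondary/tertiary care/mixed) and a random effect for study site (as a random intercept". The summary measure in Tables 5 and 6 is likewise a risk ratio adjusted only for country and site type. The two sensitivity analyses in 8.10 (complete cases, and full ITT including deaths) add no covariate.

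**Imputation.** For missing primary outcomes, 8.4 lists intervention, outcome, "age, sex, and comorbidities (diabetes, time since first CV diagnosis) and at site level, type of site and country in the imputation model". Neither LLT class nor LDL-C is included.

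**Recruitment.** Section 4.1 has DSS sites trained before they recruit. Section 4.6 accepts that allocation cannot be concealed from operational staff once made. Section 4.7 adds: "Due to the nature of the intervention the study team delivering the intervention will not be blinded". The footnote to Figure 3 says that numbers eligible and assessed are not recorded.

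**Outcome rule.** Under 5.2, a naive patient who starts on monotherapy meets the outcome only by a further step, while one started on combination therapy at discharge meets it then. A patient already on LLT meets it by any intensification from admission onward.

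**Use of baseline LLT.** It is tabulated by arm (8.3, Table 16). LLT-naive status enters 8.8 as a subgroup interaction.

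**Lipids.** The equation in 8.5.2 defines its outcome as "mean LDL-C (or other lipid measure) in mmol/L" and has BaselineLDL as its only baseline term. The code in 14.2.2 has a variable called baseline, without naming the lipid, and the Table 26 footnote names no baseline covariate.

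**LDL-C target.** Section 8.5.3 fits the LDL-C <1.4 mmol/L outcome without baseline LDL-C and states: "This analysis will be for all people with Week 16 follow-up". Section 8.5 assigns the secondary endpoints other than time to event to the intention-to-treat population, and 8.5.2 multiply imputes continuous LDL-C.

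**The concern.** Randomising sites balances sites, not the patients whom unblinded staff later approach and consent. Here the likely axis of imbalance, treatment on admission, also decides what counts as an event. If DSS sites enrol a different share of naive patients, the two arms are partly scored by different rules and the model has no term to absorb it. Without a count of eligible patients, selective enrolment cannot be checked from screening data. It would show only as a difference in baseline tables, and a covariate added after seeing that would be post hoc.

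The lipid and LDL-C target models raise lesser questions of the same kind: which baseline value is used, and in whom.

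**Working it through.** **1. The plan's own figure.** SAP 4.5 gives a "two-sided statistical test at the 5% significance level", a rise from the "SoC group of 0.05 to 0.15 in the DSS with 90% power", ICC 0.1 and 31 patients per site, and concludes: "we require 744 patients in 24 clusters within each arm".

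- Design effect: 1 + (31 − 1) × 0.1 = 4, so 744 / 4 = 186 effective patients per arm.
- Unpooled formula: 183.9 × 4 = 736, or 23.7 clusters, rounded up to 24 × 31 = 744. Pooled formula: 188 × 4 = 752. Power at 744 is 0.903 (unpooled) or 0.898 (pooled).
- 5% loss: 744 / 0.95 = 783.2, rounded up to 784 per arm, 1568 in total. 31 / 0.95 = 32.6, so 33 per site × 24 = 792 per arm, 1584 in total.

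The sample size reproduces and is not at issue.

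**2. Spurious risk ratio with no DSS effect.** The documents give no rates by LLT class and no expected imbalance, so every rate and share here is assumed. With naive share f, the arm rate is f × (naive rate) + (1 − f) × (treated rate). SoC has 55% naive and DSS 45%:

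| Naive / treated rate | SoC | DSS | Difference | RR |
|---|---|---|---|---|
| 3% / 7.4% | 0.0498 | 0.0542 | +0.44 points | 1.09 |
| 25% / 45% | 0.34 | 0.36 | +2.0 points | 1.06 |
| 20% / 60% | 0.38 | 0.42 | +4.0 points | 1.11 |

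A 5-point imbalance at 20% / 60% gives 0.38 vs 0.40 (RR 1.05). Swapping the shares of the two arms inverts the ratios: 0.0498 / 0.0542 = 0.92 and 0.38 / 0.42 = 0.90.

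**3. Effect on the test.** This was simulated under no DSS effect, with 24 sites per arm, 31 patients per site, 60% naive in SoC, and 4,000 replicates per setting. The unadjusted test was a t-test on site proportions. The adjusted test compared site ratios of observed to expected events, given naive status. Both are simpler than the SAP's mixed model. Rejection rates at nominal 5%, unadjusted (ICC 0.05 / ICC 0.1):

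| Naive / treated rate | Balanced | 10 points | 15 points |
|---|---|---|---|
| 3% / 9% | 4.5% / 4.3% | 6.0% / 5.0% | 7.5% / 6.7% |
| 10% / 30% | 4.5% / 4.6% | 9.8% / 8.1% | 15.1% / 11.8% |
| 20% / 50% | 5.5% / 5.1% | 11.7% / 10.3% | 21.3% / 15.6% |

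Adjusted for naive status, rejection was 4.2% to 5.4% and the mean RR 1.00 to 1.01 in every setting.

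**4. Precision of the primary comparison.** At 20% / 60% with 55% naive, LLT class explains 0.55 × 0.45 × 0.4² / (0.38 × 0.62) = 0.168 of the outcome variance. The variance of a site mean is proportional to 0.1 + 0.9 / 31 = 0.1290 without LLT class and 0.1 + 0.9 × 0.832 / 31 = 0.1242 with it, a fall of about 4%.

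**5. Lipids.** Take the variance of a site mean as ICC + (1 − ICC)(1 − r²) / 31, with r the correlation between a lipid's own baseline and its outcome (assumed 0.5 to 0.8). Against no baseline adjustment, the reduction is 12.8% to 32.7% at ICC 0.03 and 9.5% to 24.3% at ICC 0.05. But 8.5.2 already adjusts for baseline LDL-C, so the gain for LDL-C is zero. For total and non-HDL cholesterol, suppose their baselines correlate c = 0.8 to 0.95 with baseline LDL-C, and replace r by rc for the model as written. The further gain from using the own baseline is then about 1% (r = 0.5, c = 0.95, ICC 0.05: 0.0737 to 0.0730) to 15% (r = 0.8, c = 0.8, ICC 0.03: 0.0485 to 0.0413).

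**The case against.** The strongest defence is that the model matches its estimand. Tables 5 and 6 specify adjustment for the stratification variables, and the model does that. A reader might infer an internal contradiction, but there is none. With balanced recruitment the unadjusted test holds its level, and nothing in the documents shows that an imbalance will occur.

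The plan is also not blind to the risk. Baseline LLT is tabulated by arm, and the LLT-naive interaction in 8.8 gives contrasts within naive and treated patients that a difference in naive share cannot drive. That stands, but it yields two subgroup estimates and no overall adjusted effect.

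Four stronger readings are tempting and fail:

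- *The bias could reach 40% of the planned effect.* That sets 4 points at event rates of 38% to 42% against a 10-point effect planned from 5% to 15%. At about 5% overall, the bias is 0.44 points, roughly 4% of the planned difference, against a planned risk ratio of 3.0. Event rates may well exceed 5% because intensification is broader than combination therapy, but the two scales should not be mixed.
- *Imputation inherits the same bias.* Arm is in the imputation model and planned loss is 5%. Patients who met the outcome before loss are not missing. Omitting LLT class matters mainly if missingness depends on it.
- *Every other lipid is adjusted for the wrong analyte.* The 8.5.2 equation reads as a template written for LDL-C, and the generic baseline in the code may mean each lipid's own value. The text is ambiguous and nothing resolves it.
- *Own-baseline adjustment cuts lipid variance by 10% to 33%.* That holds only against no baseline adjustment, which is not what the SAP specifies.

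**Conclusion.** The point stands as an avoidable weakness that should be corrected before unblinding. Allocation is known at recruitment, the outcome rule differs by baseline LLT, and neither the primary model, the primary-outcome imputation model nor either sensitivity analysis contains baseline LLT class or LDL-C.

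Its size depends on assumptions that the documents cannot settle. For a 10-point difference in naive share, the spurious risk ratio is about 1.09 to 1.11 across assumed rates from 3% vs 7.4% to 20% vs 60%, with a shift of 0.4 to 4 percentage points. It is smaller where the two classes differ less. It can inflate or hide an effect, since the direction depends on which arm enrols more naive patients and on which class intensifies more often. The benefit of adjustment is protection against measured imbalance, since the precision gain is only about 4%. Adjustment cannot remove selection on unmeasured factors.

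The imputation change is minor at about 5% missing. The lipid point is a clarification that mainly helps HDL-C and triglycerides. The difference in population between 8.5 and 8.5.3 is a separate inconsistency that needs reconciling.

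**What to change.** 1. **Primary model (8.4).** Prespecify baseline LLT class (none, monotherapy, combination) and baseline LDL-C as patient-level fixed effects. Keep the stratification-only model as a sensitivity analysis. Align the summary measure in Tables 5 and 6 and the footnotes of Tables 23 and 24. Risk ratios are collapsible, so with a common effect across LLT classes the target is unchanged.
2. **Imputation (8.4).** Add the same variables so that the imputation model matches the analysis model.
3. **Lipids (8.5.2).** Replace BaselineLDL by the baseline value of the lipid analysed, and align the code and the Table 26 footnote.
4. **LDL-C target (8.5.3).** Add baseline LDL-C. Reconcile the population with 8.5 by using the same multiple imputation as for continuous LDL-C.

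The cost is a SAP amendment covering text, tables and code. The variables are already collected, and 9.1 has a rule for missing baseline values. The downside is that the log-binomial model may fail to converge more often. The modified Poisson fallback would then be used more, and its wording in 8.4 should say that it accounts for clustering by site.

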14.1. Primary Outcome

```
// Load the data
use "datafile.dta", clear

// Set the maximum number of iterations
set maxiter 1000

// Fit the mixed log-binomial regression model
glm outcome intervention country site_type, family(binomial) link(log) vce(cluster site)
robust

// Display the results
estimates table
```

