# Fit model to each of the 5 imputed data sets
> fit.imp <- with(data = imp.list, lmer(outcome ~ intervention + example1 + example2
(1|clus)))

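### The primary analysis fallback does not say how site is handled, and the example code neither fits the stated model nor yields the pooled risk ratio

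*SAP*

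**What the plan says.** - **SAP 8.4, main model.** A log-binomial mixed model with fixed effects for country and site type and "a random effect for study site (as a random intercept"). The equation printed below it has a site term and two dummies each for country and site type.
- **SAP 8.4, fallback.** On non-convergence, "Poisson regression with robust standard errors (modified Poisson regression) will be used". The clause names neither a random effect nor clustering.
- **SAP 8.4, test.** "For primary analysis hypotheses will be tested as two-sided with a significance level of 0.05".
- **SAP 8.5.3.** The secondary binary outcomes are to follow the primary approach. Here the random site intercept is attached to both the log-binomial and the modified Poisson option.
- **Table 23 footnote.** Study site is listed among the adjustments to the primary risk ratio.
- **Appendix D, 14.1, repeated in 14.2.3.** A comment announces a mixed model, but the command is "glm outcome intervention country site_type, family(binomial) link(log) vce(cluster site"). It has no random effect, and country and site type are entered without factor notation.
- **Appendix D, 14.3.** The outcome is made a factor, the analysis step is "lmer(outcome ~ intervention + example1 + example2", and its coefficients are pooled.
- **Status of the imputed result.** Sections 7.1 and 8.4 make the multiply imputed analysis the primary one. Section 8.4 pools it with the R package mitools, and Tables 5 and 23 require a risk ratio.

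No section names a small-sample correction or reference degrees of freedom for 48 sites.

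**The concern.** In a cluster randomised trial, the validity of the primary test depends on how between-site variation enters the standard error. For one analysis this SAP gives three accounts: silence (8.4 fallback), a random intercept (8.5.3), and a single-level model with clustered variance (14.1). The SAP itself expects that the log-binomial mixed model may not converge, so the fallback is a live possibility.

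A clustered sandwich variance is also known to be too small with a moderate number of clusters, and nothing in the SAP corrects for that. Finally, the primary result is the pooled one, and the only pooling code fits a model on a different scale from the estimand.

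**Working it through.** **Inputs (SAP 4.5).** Rates, power and size per arm: "difference in proportions from the SoC group of 0.05 to 0.15 in the DSS with 90% power, we require 744 patients in 24 clusters". Test, ICC and site size: "two-sided statistical test at the 5% significance level, ICC of 0.1 and clusters of a similar size (31 for each site"). For the lower ICCs: "In the database we examined the hypertension guideline interventions, these varied from 0.048 to 0.064".

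**1. Reproduce the plan's figure.** Design effect = 1 + (31 − 1) × 0.1 = 4.0. Unpooled n per arm = (1.960 + 1.282)² × (0.05 × 0.95 + 0.15 × 0.85) / 0.10² = 183.9. Then 183.9 × 4 = 735.5, and 735.5 / 31 = 23.7, rounded up to 24 sites × 31 = 744. With 5% loss, 744 / 0.95 rounds up to 784 per arm, or 1568 in total; 33 per site × 48 = 1584. The sample size is reproduced, so a design effect of 4 is the plan's own working figure.

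**2. Fallback run without clustering.** The variance is understated by the design effect (DE), so type I error = 2 × [1 − Φ(1.96 / √DE)].

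| Patients per site | ICC | DE | Type I error |
|---|---|---|---|
| 31 | 0.048 | 2.44 | 21.0% |
| 31 | 0.064 | 2.92 | 25.1% |
| 31 | 0.1 | 4.0 | 32.7% |
| 33 | 0.1 | 4.2 | 33.9% |

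**3. Simulation under no effect.** There were 48 sites and 4,000 replicates per scenario. The fitted model was log-link Poisson with arm, two country dummies and two site-type dummies, which is 6 parameters and leaves 48 − 6 = 42 df. The clustered variance includes the factor 48/47. Monte Carlo error is about 0.3 to 0.8 points.

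| Event rate | ICC | Per site | Size CV | Robust, no clustering | Clustered, z | Clustered, t(42) | Mancl-DeRouen, t(42) |
|---|---|---|---|---|---|---|---|
| 5% | 0.1 | 31 | 0 | 32.3% | 8.3% | 7.4% | 4.5% |
| 5% | 0.1 | 33 | 0 | 33.1% | 7.9% | 7.0% | 4.2% |
| 5% | 0.05 | 31 | 0 | 22.4% | 8.6% | 7.6% | 4.8% |
| 15% | 0.1 | 31 | 0 | 32.9% | 7.4% | 6.7% | 4.1% |
| 40% | 0.1 | 31 | 0 | 32.0% | 6.9% | 6.0% | 3.5% |
| 5% | 0.1 | 31 | 0.5 | 35.6% | 10.4% | 9.3% | 4.3% |
| 40% | 0.1 | 31 | 0.5 | 37.3% | 8.1% | 7.2% | 3.4% |

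The simulation agrees with the formula in step 2. A t reference alone removes only part of the excess in the clustered test.

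**4. Does the risk ratio target move?** With a log link and a site effect U independent of arm, E[exp(β₀ + β₁x + U)] = exp(β₀ + β₁x) × E[exp(U)]. The last factor cancels in the ratio, so the conditional and marginal risk ratios coincide. Replacing the random intercept by clustered variance changes the standard error, interval and p-value, not the target.

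**5. The 14.3 step.** `lmer` is a linear mixed model, so its arm coefficient is a risk difference. At the design rates this is 0.15 − 0.05 = 0.10, whereas the log risk ratio is ln(0.15 / 0.05) = 1.10. As printed, the step would not run: the outcome is a factor, and there is no plus sign before the random term.

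**The case against.** The best defence is that the SAP never removes site.

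- Section 8.4 is silent in one clause, and the equation below that clause carries a site effect.
- Section 8.5.3 says it restates the primary approach and keeps site in both options. The Table 23 footnote and the 14.1 command keep site too.
- Appendix D is headed as example code and uses placeholder names. Section 8.4 is the specification, and it has the right dummies and scale.
- Section 4.5 calls the ICC of 0.1 conservative and plans sites of similar size.

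Much of this stands. A reader might infer that the fallback drops clustering and that the trial therefore runs a one-in-three false-positive risk. The documents do not support that: the 33% belongs to a literal reading that three other places point against. A reader might also infer that a risk ratio of 3.0 would be reported as exp(0.10) = 1.11. Nothing in the SAP exponentiates that coefficient, and the step fails before producing one.

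The choice of correction is partly preference. In a separate simulation on similar assumptions, Kauermann-Carroll with t on 42 df gave 4.8 to 6.6%, and Mancl-DeRouen gave 3.2 to 4.8%.

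What the defence does not answer is that the passages still differ, no small-sample rule exists, the printed primary code is not the stated model, and no code yields the pooled risk ratio.

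**Conclusion.** The point holds as under-specification and inconsistency, and it should be corrected before analysis. Depending on which passage is followed, the fallback's type I error ranges from about 33% (no clustering, ICC 0.1) to about 7 to 8% (clustered z-test, ICC 0.1, equal sites) or 8 to 10% (site sizes varying). The corrected test gave 3.4 to 4.8% in every scenario in the table.

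The broader claim that the primary p-value, interval and risk ratio will all be wrong is not supported. It would require the example code or the unclustered reading to replace the text, and only the `lmer` step alters the effect measure.

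Assumptions not in the documents are beta-binomial site variation, a random site-type mix, the size CV of 0.5 and the 40% event rate. The simulated fits used Poisson with dummies, so they stand in for the printed log-binomial command with single linear terms and do not run it exactly. The random-intercept log-binomial model was not tested, so nothing here speaks to its own error rate.

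**What to change.** - **8.4:** state that the fallback is modified Poisson regression with standard errors clustered on site, Mancl-DeRouen bias-corrected, with a t reference on 48 minus the number of model parameters (42 df). Apply the same rule to any cluster-robust result, and reword 8.5.3 to match.
- **14.1 and 14.2.3:** fit the stated log-link model with its random site intercept, and use factor notation for country and site type. A single linear term for a three-level factor does not match the equation.
- **14.3:** fit that same log-link model in each imputed dataset and pool the log risk ratios.
- **Section 10:** if the correction is run in R, extend the software statement, which now reserves R for imputation.

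The cost is text and code edits, plus wider intervals than the uncorrected ones. With equal leverage of 6/48 = 0.125 per site, the standard error grows by 1 / (1 − 0.125) = 1.143. The critical value grows by 2.018 / 1.960 = 1.030, and the factor √(48/47) = 1.011 drops out. The net is 1.143 × 1.030 / 1.011 = 1.16, so about 16% wider, and more if site sizes vary; Kauermann-Carroll would give √1.143 × 1.030 / 1.011 = 1.09. Much of this restores width that the uncorrected interval lacks. Moving from z to t on 42 df changes the planned power at 744 per arm from 0.903 to 0.890.
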